### **Prohibited medications**

Subjects should not receive other anti-cancer therapy [cytotoxic, biologic, radiation, or hormonal (other than leuprolide or other GnRH agonists)] while on treatment in this study.

Medications that inhibit CYP3A4 may result in increased plasma Pazopanib concentrations; therefore, co-administration of strong CYP3A4 inhibitors is PROHIBITED beginning 14 days prior to the first dose of study drug until discontinuation from the study.

Strong CYP3A4 inhibitors include (but are not limited to):

- Antibiotics: clarithromycin, telithromycin, troleandomycin
- HIV: protease inhibitors (ritonavir, indinavir, saquinavir, nelfinavir, lopinavir)
- Antifungals: itraconazole, ketoconazole, voriconazole
- Antidepressants: nefazodone

#### **7.4.1. Specific recommendations regarding anticoagulants**

Results from drug-drug interaction studies conducted in subjects with cancer suggest that Pazopanib has no effect on the metabolism of S-warfarin. Hemorrhagic events, however, have been reported in clinical studies with Pazopanib; therefore, Pazopanib should be used with caution in subjects with increased risk of severe bleeding or who are receiving concomitant anticoagulant therapy (e.g., warfarin or its derivatives, low molecular weight heparin, unfractionated heparin). Subjects taking concomitant anticoagulant therapy should be monitored regularly for changes in relevant coagulation parameters as clinically indicated, as well as for any clinical bleeding episodes.

#### **7.4.2. Specific recommendations regarding hypoglycemic therapy including insulin**

Results from drug-drug interaction studies conducted in subjects with cancer suggest that there will be no clinically relevant pharmacokinetic interaction between Pazopanib and hypoglycemic agents. Transient decreases in serum glucose (mainly Grade 1 and 2, rarely Grade 3) have been observed in clinical studies with Pazopanib. In addition, decreases in blood sugar have been recently reported in subjects treated with another small molecule tyrosine kinase inhibitor, sunitinib (Billefont, 2008). Such changes may

require an adjustment in the dose of hypoglycemic and/or insulin therapy. Subjects should be advised to report symptoms of hypoglycemia (e.g., confusion, visual disturbances, palpitations, sweating). Serum glucose should be tested during treatment with Pazopanib as outlined in the protocol and as clinically indicated.

### 7.4.3. The Effects of Pazopanib on Other Drugs

In vitro data indicate that Pazopanib is a potential inhibitor for CYP3A4, CYP2C8, CYP2D6, CYP1A2, CYP2C9, CYP2C19, CYP2A6, CYP2B6, and CYP2E1. Pregnane X receptor transient transfection assay suggested some potential for human CYP3A4 induction at high concentrations. Results from drug-drug interaction studies conducted in subjects with cancer suggest that Pazopanib is a weak inhibitor of CYP3A4, CYP2C8, and CYP2D6 in vivo, but had no clinically relevant effect on CYP1A2, CYP2C9 or CYP2C19 metabolism. Therefore, concomitant use of Pazopanib with certain medications (substrates of CYP3A4, CYP2C8, and CYP2D6) with a narrow therapeutic window should be undertaken with **CAUTION** due to the potential for alterations in the pharmacological effects of these medications or an increased risk for serious or life threatening adverse events associated with such medications (see below) secondary to the inhibition of specific CYP enzymes by Pazopanib. In addition, the potential for drug interaction with such medications, although diminished, may persist after the last dose of Pazopanib due to its long half-life (i.e., mean 30.9 hours); therefore, continue to exercise **CAUTION** for at least 7 days and up to 15 days after the last dose of Pazopanib when administering these medications. These medications include (but are not limited to):

- Ergot derivatives: dihydroergotamine, ergonovine, ergotamine, methylergonovine (potential increased risk for developing ergot toxicity that includes severe vasospasm leading to peripheral as well as cerebral ischemia)
- Neuroleptics: pimozide (potential increased risk for QT interval prolongation, ventricular arrhythmia, and sudden death)
- Antiarrhythmics: bepridil, flecainide, lidocaine, mexiletine, amiodarone, quinidine, propafenone (potential increased risk for QT interval prolongation and Torsade de Pointes)
- Immune modulators: cyclosporine, tacrolimus, sirolimus (potential increased risk for nephrotoxicity and neurotoxicity)
- Miscellaneous: quetiapine, risperidone, clozapine, atomoxetine.

### 7.4.4. The Effects of Other Drugs on Pazopanib

Results from in vitro studies suggest that the oxidative metabolism of Pazopanib in human liver microsomes is mediated primarily by CYP3A4, with minor contributions from CYP1A2 and CYP2C8. Furthermore, in vitro data suggest that Pazopanib is a substrate for p-glycoprotein. Substances that induce or inhibit CYP3A4 may alter the pharmacological effects of Pazopanib and should be used with **CAUTION**.

Medications that inhibit CYP3A4 may result in increased plasma Pazopanib concentrations. Co-administration of strong CYP3A4 inhibitors is prohibited (see Section on Prohibited Medications); therefore selection of an alternate concomitant medication with no or minimal potential to inhibit CYP3A4 is recommended.

CYP3A4 inducers may decrease plasma Pazopanib concentrations. Selection of an alternate concomitant medication with no or minimal enzyme induction potential is recommended. Drugs that induce CYP3A4 and may decrease Pazopanib plasma

concentrations include (but are not limited to):

- Glucocorticoids: cortisone (>50 mg), hydrocortisone (>40 mg), prednisone (>10 mg), methylprednisolone (>8 mg), dexamethasone (>1.5 mg)
- Anticonvulsants: phenytoin, carbamazepine, phenobarbital, oxcarbazepine
- HIV antivirals: efavirenz, nevirapine
- Antibiotics: rifampin (rifampicin), rifabutin, rifapentene
- Miscellaneous: St. John's Wort, modafinil, pioglitazone

### ***7.5. Treatment of Investigational Product Overdose***

No maximum tolerated dose (MTD) was reached in dose escalation studies of Pazopanib administered as a single agent at doses of up to 2000 mg/day. Pazopanib exposure at higher doses appeared to reach a plateau level at a dose of 800 mg daily.

In the event of overdose (defined as administration of more than the protocol-specified dose), the investigator should contact [REDACTED] and additional monitoring of the subject for AEs/SAEs and laboratory abnormalities should be considered. Decisions regarding dose interruptions or modifications will be made by the investigator in consultation with the GEIS Study Chair based on the clinical evaluation of the subject. Information regarding the quantity of the excess dose should be documented in the CRF.

## 7.6. Criteria for regimen modification during the study

### 7.6.1. Dose Interruptions/Modifications for Specific, Non-liver Related, Toxicities

As a general rule, if dose reduction of IP is necessary, the dose should be reduced stepwise by 200 mg at each step, and the subject should be monitored for approximately 10 to 14 days at each dose level. If toxicity does not abate during this monitoring time, the IP may need to be interrupted and/or the dose further decreased with continued monitoring for an additional 10-14 days at each dose level, and so on.

If the toxicity has abated with reduction of the dose and dose re-escalation is considered safe by the investigator, the IP dose can then be increased step-wise back to the pre-event dose (in 200 mg increments, after monitoring for 10-14 days at each dose level to ensure that toxicity did not recur or worsen).

If a subject's treatment has been interrupted for more than 21 days, the Investigator must contact the Trial Chief Investigator by email [REDACTED] to review the subject's condition in order to resume the treatment.

Recommendations for investigational product dose interruptions/modifications in case of specific treatment-emergent AEs are provided in the following Table

**Table 2: Dose Modification Algorithms for Potential Treatment-Related Adverse Events**

AE Terms & Descriptions	Dose Modification Algorithms
Hypertension	
(A). Asymptomatic and persistent SBP of $\geq 140$ and $<170$ mmHg, or DBP $\geq 90$ and $<110$ mmHg, or a clinically significant increase in DBP of 20 mmHg (but still below 110 mmHg).	Step 1. Continue investigational product (IP) at the current dose. Step 2. Adjust current or initiate new antihypertensive medication(s). Step 3. Titrate antihypertensive medication(s) during next 2 weeks as indicated to achieve well-controlled blood pressure (BP). If BP is not well-controlled within 2 weeks, consider referral to a specialist and go to scenario (B).
(B). Asymptomatic SBP $\geq 170$ mmHg, or DBP $\geq 110$ mmHg, or failure to achieve well-controlled BP within 2 weeks in scenario (A).	Step 1. Consider reducing or interrupting IP, as clinically indicated. Step 2. Adjust current or initiate new antihypertensive medication(s). Step 3. Titrate antihypertensive medication(s) during next 2 weeks as indicated to achieve well-controlled BP. Step 4. Once BP is well-controlled, restart IP dose-reduced by 200 mg if IP was interrupted.
(C). Symptomatic hypertension or recurring SBP $\geq 170$ mmHg, or DBP $\geq 110$ mmHg, despite modification of antihypertensive medication(s)	Step 1. Interrupt IP Step 2. Adjust current or initiate new antihypertensive medication(s). Step 3. Titrate antihypertensive medication(s) during next 2 weeks as indicated to achieve well-controlled BP. Referral to a specialist for further evaluation and follow-up is also recommended. Step 4. Once BP is well-controlled, restart IP dose-reduced by 200 mg.

(D). Refractory hypertension unresponsive to above interventions.	Discontinue IP and continue follow-up per protocol.
Prolongation of QTc Interval: If the QTc is prolonged, the ECG should be manually read to ensure accuracy of the reading. The values below refer to manually-read ECGs.	
QTc $\geq$ 480 < 500 msec	Continue IP; monitor as clinically indicated.
QTc $\geq$ 500 msec	Discontinue IP and continue follow-up per protocol.
Proteinuria	
UPC <3	Continue Pazopanib at the current dose; monitor as clinically indicated
UPC $\geq$ 3 or 24-h urine protein $\geq$ 3g	
Step 1. Interrupt IP.
 
Step 2. Weekly UPC or 24-hr urine protein monitoring until UPC is <3 or 24-hr urine protein is <3 grams. Then restart Pazopanib dose-reduced by 200 mg.
 
Step 3. If UPC <math>\geq</math>3 or 24-h urine protein <math>\geq</math> 3g recurs, repeat steps 1 and 2.
 
Step 4. If UPC <math>\geq</math>3 or 24-hr urine protein <math>\geq</math>3 recurs and the Pazopanib dose can no longer be reduced, discontinue Pazopanib and continue follow-up per protocol.

Hemorrhage /Bleeding: Investigate and document underlying etiology of the bleeding	
Grade 1	
For hemoptysis, interrupt Pazopanib and contact Chief Study Physician to discuss whether further treatment with Pazopanib is appropriate.
 
For other Grade I haemorrhage/bleeding events, continue Pazopanib at the current dose; monitor as clinically indicated.

Grade 2	
Step 1. If pulmonary or GI bleed (other than hemorrhoidal bleeding), discontinue IP and continue follow-up per protocol. Otherwise, interrupt IP until the AE resolved to <math>\leq</math> Grade 1.
 
Step 2. Restart IP; consider reducing dose and monitor as clinically indicated.

Grade 3 or 4, or Recurrent $\geq$ Grade 2 event after dose interruption/reduction.	Discontinue IP and continue with follow-up per protocol.
Venous Thrombosis (DVT, PE)	
Grade 2	Continue IP at the current dose; monitor as clinically indicated
Grade 3	
Step 1. Interrupt IP.
 
Step 2. Initiate and monitor anticoagulation as clinically indicated.
 
Step 3. Resume IP at reduced dose only if all of the following criteria are met:
 
 
• The subject must have been treated with anticoagulant at the desired level of anticoagulation for at least one week.
 
• No Grade 3 or 4 or clinically significant Grade 2, hemorrhagic
 

[figure not shown]
	
events have occurred while on anticoagulation treatment.
 
Subject should be monitored as clinically indicated during anticoagulation treatment and after resuming study treatment. When treating with warfarin, international normalized ratio (INR) should be monitored within three to five days after any change in IP dosing (eg, re-initiating, escalating/de-escalating, or discontinuing IP), and then at least weekly until the INR is stable. The dose of warfarin (or its derivatives) may need to be adjusted to maintain the desired level of anticoagulation

Grade 4 and/or PE	Discontinue IP and continue follow-up per protocol.
Arterial Thrombosis/Ischemia	
Any Grade	Discontinue IP and continue follow-up per protocol.
Thrombocytopenia: Investigate and document underlying cause	
Grade 1 or 2	Continue IP with current dose; monitor as clinically indicated.
Grade 3 or 4	
Step 1. Interrupt IP until toxicity resolves to <math>\leq</math> Grade 2.
 
Step 2. Restart IP dose-reduced by 200 mg and monitor as clinically indicated.
 
If no recovery to <math>\leq</math> Grade 2 or recurrent Grade 3 or 4 thrombocytopenia, discontinue IP and follow-up per protocol.

Anemia: No specific dose reduction rules are indicated for anemia unless due to hemorrhage or bleeding as noted above.	
Palmar-plantar Erythrodysesthesia Syndrome	
Grade 1 Minimal skin changes or dermatitis without pain (erythema, oedema, hyperkeratosis)	Continue IP at present dose
Grade 2 Skin changes with pain; limiting instrumental activities of daily living (ADLs) (peeling, blisters, oedema, bleed, hyperkeratosis)	
 
1. Hold IP
 
2. Treat as clinically appropriate
 
3. Upon resolution to Level 1 or better restart IP with a dose reduction to 400 mg
 
4. If recurrent consider a further dose reduction to 200mg or discontinuation
 

Grade 3 Severe skin changes with pain and limiting self care ADLs	Discontinue IP
Other Clinically Significant Adverse Eventsb	
Grade 1	Continue IP; monitor as clinically indicated.
Grade 2 or 3, if clinically significant	
Step 1. Interrupt IP until toxicity resolves to <math>\leq</math> Grade 1.
 
Step 2. Restart IP dose-reduced by 200 mg and monitor as clinically indicated.

Grade 4	Discontinue IP and continue follow-up per protocol.

- Well-controlled BP defined as SBP <140 mmHg and mean DBP <90 mmHg.
- AEs are graded according to NCI Common Terminology Criteria for Adverse Events

---

v4.0 (NCI CTCAE v4)  
Abbreviations: BP, blood pressure; IP, investigational product.

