## **7. TREATMENT DESCRIPTION**

### **7.1. Study Medication**

Pazopanib is an oral tyrosine kinase inhibitor of the VEGFR, PDGFR and KIT with a dual activity both as an antiangiogenic and also and anti-tumoral agent.

The investigational product, Pazopanib monohydrochloride salt is produced as tablets containing Pazopanib monohydrochloride salt equivalent to 200 mg or 400 mg of the free base. Refer to the Pazopanib SPC for information regarding the physical and chemical properties of Pazopanib and a list of excipients.

Investigational product must be stored in a secure area under the appropriate physical conditions for the product (Pazopanib does not require any special storage conditions). Access to and administration of the investigational product will be limited to the investigator and authorized site staff. Investigational product must be dispensed or administered only to subjects enrolled in the study and in accordance with the protocol.

Investigational product (Pazopanib) should begin within 7 days of inclusion (longer delays must be discussed with Study Chair by email: [REDACTED]).

Pazopanib 800 mg (2x400mg or 4x200 mg) per day (once a day) should be taken orally without food at least 1 hour before or at least 2 hours after a meal. The time of day for administration of Pazopanib should be relatively constant, but does not need to be recorded on the CRF. If a subject misses a dose, the subject should take the dose as soon as possible, but not less than 12 hours before the next dose is due. If the next dose is due in less than 12 hours, the subject should skip the missed dose and take the next dose as scheduled.

Pazopanib will be provided to sites by the Sponsor through [REDACTED]. The contents of the investigational product label will be in accordance with all applicable regulatory requirements.

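### The Grade 2 palmar-plantar row restarts pazopanib at a fixed 400 mg, which is not a reduction for a patient already at 400 or 200 mg

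*Protocol*

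**What the plan says.** Patients start at 800 mg once daily. Protocol section 7.6.1 sets the default for lowering the dose: "As a general rule, if dose reduction of IP is necessary, the dose should be reduced stepwise by 200 mg at each step". Table 2 follows, introduced as recommendations for specific adverse events.

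For Grade 2 palmar-plantar erythrodysesthesia (painful skin changes that limit instrumental daily activities), the row has four steps: hold the drug, treat, then "Upon resolution to Level 1 or better restart IP with a dose reduction to 400 mg", and finally "If recurrent consider a further dose reduction to 200mg or discontinuation". Grade 3 leads straight to discontinuation.

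Other rows express the cut relative to the current dose. The proteinuria row says "Then restart Pazopanib dose-reduced by 200 mg". If the event "recurs, repeat steps 1 and 2" applies, and if it "recurs and the Pazopanib dose can no longer be reduced, discontinue Pazopanib" applies. The hypertension and thrombocytopenia rows, and the row for other events of "Grade 2 or 3, if clinically significant", also use a 200 mg cut. Section 7.1 describes the supply as "tablets containing Pazopanib monohydrochloride salt equivalent to 200 mg or 400 mg of the free base".

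**The concern.** Step 3 of the palmar-plantar row names a target dose without saying where the patient starts from. It reads as if every first event happens at 800 mg, or at least above 400 mg. A patient already lowered for hypertension, proteinuria or another toxicity can have a first Grade 2 skin event at 400 or 200 mg. Step 4 does not help, because it applies only to recurrence.

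This is a narrow patient-safety point. The row is meant to lower exposure after a painful, function-limiting toxicity. At 400 mg, followed as printed, it restarts the same dose. At 200 mg it cannot be followed as a reduction. Sites would have to improvise and could do so differently.

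**Working it through.** The protocol states no figure to reproduce here, so the check is arithmetic on the dose levels.

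**Inputs**
- Starting dose: 800 mg once daily (Protocol 1.10).
- General step: 200 mg (7.6.1), which gives levels of 800, 600, 400 and 200 mg.
- Restart dose after a first Grade 2 palmar-plantar event: 400 mg (Table 2, step 3).
- Smallest tablet: 200 mg (7.1).

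**Formulas**
- Change under the row = 400 - dose at onset; percent change = change / dose at onset.
- Dose under the general rule = dose at onset - 200.
- Earlier 200 mg cuts needed to be at that dose = (800 - dose at onset) / 200.

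| Dose at onset | Earlier cuts needed | Change under the row | Percent | General rule gives |
|---|---|---|---|---|
| 800 mg | 0 | 400 - 800 = -400 mg | -50.0% | 600 mg |
| 600 mg | 1 | 400 - 600 = -200 mg | -33.3% | 400 mg |
| 400 mg | 2 | 400 - 400 = 0 mg | 0.0% | 200 mg |
| 200 mg | 3 | 400 - 200 = +200 mg as printed | not a reduction | 0 mg |

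At 800 mg the row cuts by two general steps at once, which can be a deliberate exception. At 600 mg the row and the general rule agree. The row stops working at 400 mg and below. The +200 mg entry only shows that the printed number is not a reduction; the word itself rules out an intended increase.

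**Can a patient be at 400 or 200 mg beforehand?** Yes. The proteinuria row alone takes 800 to 600, 400 and then 200 mg over three episodes. Cuts for different toxicities also add up: one for hypertension and one for proteinuria bring a patient to 400 mg.

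**Do other rows say what happens when no cut is left?** The proteinuria row does so explicitly. The hypertension, bleeding and thrombocytopenia rows end in discontinuation for refractory or recurrent events. The Grade 2 or 3 row for other clinically significant events has the 200 mg cut but no recurrence or floor rule. The palmar-plantar row has an end point for recurrence only.

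**The case against.** The strongest reply is that section 7.6.1, read as a whole, already gives a safe path. Table 2 is labelled as recommendations. A site that sees a call for a reduction in a patient at 400 mg would apply the general step and go to 200 mg. At 200 mg only stopping is left, and section 6.3.1 provides for permanent discontinuation when toxicity is unacceptable or when the investigator judges continued dosing too risky. Step 1 of the row holds the drug until the event improves, so nobody is dosed through active Grade 2 skin toxicity. A floor of 200 mg can be inferred from the tablet strengths, step 4 and the proteinuria row. Re-escalation is allowed, so some patients will be back at a higher dose by the time of the event.

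Much of this stands, and it limits the weight of the point. At 400 mg the fallback is reasonable, although the row does not refer to the general rule and already departs from it at 800 mg, so a site cannot be sure which governs. At 200 mg the fallback fails, because the general step gives 0 mg and stopping is left to judgement. The proteinuria row shows that a written stop rule was thought worthwhile elsewhere in the same table. The hold protects the patient until resolution, but the gap is the dose after resolution.

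**Conclusion.** The concern holds. Taken as written, step 3 gives a true reduction at 800 and 600 mg, no change at 400 mg and no valid instruction at 200 mg, so it fails at 2 of 4 dose levels. With the general rule as a fallback, only the 200 mg case is left without any dose or written stop rule.

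Counting dose levels does not measure how many patients are affected. A failing case needs two net earlier 200 mg cuts (for 400 mg) or three (for 200 mg) for other toxicities, followed by a first Grade 2 palmar-plantar event. The documents give no frequency for that sequence; it is assumed to be uncommon.

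This is a low-priority change: worth making because it concerns patient safety and costs almost nothing. It has no bearing on the 12-week endpoint, the sample size or the Simon decision rules.

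**What to change.** Reword step 3 so that the restart dose is always below the dose at onset, for example: restart at 400 mg if the dose at onset was above 400 mg; if it was 400 mg, restart at 200 mg or discontinue; if it was 200 mg, discontinue. The resulting changes are -50% from 800 mg, -33% from 600 mg, -50% or stop from 400 mg, and stop from 200 mg. The clinical team should confirm these doses.

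Add one sentence to section 7.6.1: 200 mg is the lowest dose level, and pazopanib is discontinued if a further reduction is required at that level. Its main use outside this row is for the Grade 2 or 3 row for other clinically significant adverse events, which has no floor of its own.

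The cost is one table cell and one sentence of protocol wording, with no change to any statistical parameter.

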## 7.6.2. Dose Interruptions/Modifications for Hepatotoxicity

Patients over 60 years of age have an increased risk of ALT > 3 x ULN.

Concomitant use of pazopanib and simvastatin increases the risk of ALT elevations and should be undertaken with caution and close monitoring.

Recommendations for IP dose interruptions/modifications in case of liver-related treatment-emergent AEs are provided in Table 3. As a general rule, since many subjects are taking multiple concurrent medications, it is critical to:

- (a) do a thorough evaluation of the subject's concurrent medications (and ensure all are recorded in the eCRF), and
- (b) identify and discontinue those with known hepatotoxicity and replace with a non-hepatotoxic equivalent for the same indication if necessary.

Record alcohol use on the liver event alcohol intake form in the eCRF. Liver dysfunction must be fully evaluated even if clinical signs and symptoms indicate progression of liver tumor lesions. Imaging studies must be obtained to document potential progression of malignancy.

